3.5.1.6 Main Study: Interventional Phase (Day 1 to Day 180)

After the baseline visit, there are no mandated visits until Day 180. However, it is anticipated that patients will undergo medical evaluation at regular intervals. Data collected at these routine care visits, such as Abilify MyCite use changes and AEs (as described in [Section 4](#)), will be entered into the study database. Physicians are expected to regularly review the Abilify MyCite dashboard data during active Abilify MyCite use as consistent with routine care, approximately every 2 weeks.

At the time points indicated in [Table 3.5.1-1](#), the patient, caregiver (if applicable), and physician outcomes scales will be completed.

3.5.1.7 Main Study: Day 180 Mid-study (or End-of-study) Visit

The Day 180 visit marks the end of the interventional phase. All patients will complete the Day 180 visit. Data collected at the Day 180 visit, such as Abilify MyCite use changes and certain AEs (as described in [Section 4](#)), will be entered into the study database. CCI

At the Day 180 visit, a second, optional interventional period (up to 6 months of Abilify MyCite; Days 180-≤360) may be initiated per the joint decision of the patients with their study physician; if the patient is not continuing into the optional period, then the Day 180 visit is the final visit. During this second, optional interventional period, patients may start and stop Abilify MyCite as clinically indicated.

If a patient withdraws or is withdrawn from the study prematurely (eg, before completing the scheduled Day 180 visit), then an early ET visit should be performed, at which time all assessments and procedures that were to have been performed at the Day 180 visit should be completed. In such cases, the reason for the ET must be recorded.

3.5.1.8 Main Study: Second Interventional Period (Day 180 to Day 360)

At the Day 180 visit (or later during the Day 180-<360 period), patients will decide jointly with their study physician whether to restart Abilify MyCite for a second interventional period (Days 180-≤360). Patients will re-initiate Abilify MyCite at Day 180 (or later during the Day 180-<360 period) and the second interventional period

will proceed similarly to the interventional period described in [Section 3.5.1.6](#). Data collected at routine care visits between Day 180 and Day 360, such as Abilify MyCite use changes and AEs (as described in [Section 4](#)), will be entered into the study database. Physicians are expected to regularly review the Abilify MyCite dashboard data during active Abilify MyCite use as consistent with routine care, approximately every 2 weeks. Note that patients need to be on aripiprazole to use the system for the optional second treatment period.

CCI [REDACTED]

If a patient withdraws or is withdrawn from the study prematurely (eg, before completing the scheduled Day 360 visit), then an early ET visit should be performed, at which time all assessments and procedures that were to have been performed at the Day 360 visit should be completed. In such cases, the reason for the ET must be recorded.

3.5.1.9 CCI [REDACTED]

[REDACTED]

Additional patient data will be collected if available per routine clinical practice, eg, prior (up to 12 months) hospitalizations (all-cause and psychiatric) and concomitant medications.

3.5.2 Exploratory Study: Schedule of Assessments

Study assessment time points for enrolled patients are summarized for the exploratory study in [Table 3.5.2-1](#).

Procedures for the exploratory study will be similar to those in the main study ([Section 3.5.1.1](#) through [Section 3.5.1.5](#), and [Section 3.5.1.9](#)), with the exception that there will be 1-month intervals of Abilify MyCite use (and 1-month intervals of prohibition of Abilify MyCite use), as diagrammed in the study schematic ([Figure 3.1-3](#)). During periods of nonuse of Abilify MyCite, the patient continues with oral aripiprazole, per routine clinical care. If the patient goes on another (non-aripiprazole) treatment, data will be collected, but the patient will not return to Abilify MyCite if that treatment is not appropriate.

Protocol 316-13-217

For the exploratory study, the site visits will be at screening, baseline (which may be the same day as the screening visit), Day 180, and Day 360; additional visits are to occur as clinically indicated, and assessments will occur at the times indicated in [Table 3.5.2-1](#).

Table 3.5.2-1 Exploratory Study: Schedule of Assessments (for Patients Enrolled at Sites)								
	Screening ^a	Interventional Phase ^b					End-of-study Visit ^c	CCI
	≤13 days ^a	Baseline (Day 1) ^a	Day 30±7	Day 60±7	Day 180±7	Day 300±7	Day 360±7	Days 1- 360
Study site visit	X	X			X		X	
Informed consent	X							
Inclusion/exclusion criteria assessment	X							
Smartphone and data plan verification	X							
Demographic information and medical / psychiatric history		X						
Height and weight measured		X						
Vital signs		X						
Onsite onboarding with Abilify MyCite; patient pairs and applies patch		X						
Dispense patches, aripiprazole + IEM, and other supplies ^d		X	----x----	----x----	----x----	----x----	----x----	
Physician reviews Abilify MyCite dashboard data every 2 weeks ^e			----x----	----x----	----x----	----x----	----x----	
CCI			█	█		█		
			█	█		█		
			█	█		█		
			█	█		█		
		█			█		█	

Table 3.5.2-1 Exploratory Study: Schedule of Assessments (for Patients Enrolled at Sites)								
	Screening ^a	Interventional Phase ^b					End-of-study Visit ^c	CCI
	≤13 days ^a	Baseline (Day 1) ^a	Day 30±7	Day 60±7	Day 180±7	Day 300±7	Day 360±7	Days 1- 360
Concomitant medications								X ^g
Hospitalizations (all-cause and psychiatric)								X ^g
CCI								

Seq = Sequence.

^aThe screening and baseline visits can be combined.

^bThe interventional period begins with the baseline visit and ends at the Day 360 visit (or ET if the patient withdraws or is withdrawn from the study prematurely). Clinical data will be collected as part of routine clinical practice, not as a requirement for the protocol.

^cAll patients will complete the Day 360 visit. If a patient withdraws or is withdrawn from the study prematurely (eg, before completing the scheduled Day 360 visit), then an early ET visit should be performed, at which time all assessments and procedures that were to have been performed at the Day 360 visit should be completed. In such cases, the reason for the ET must be recorded.

^dThe physician will dispense Abilify MyCite supplies (patches, aripiprazole + IEM, and other supplies) during routine visits as required during the study per Sequences 1 and 2. Note that “----x----” indicates the activity can occur multiple times during the period.

^eThe study physician is expected to regularly review the Abilify MyCite dashboard data during active Abilify MyCite use as consistent with routine care, approximately every 2 weeks. Note that “----x----” indicates that the activity will occur multiple times during the period.

^fIf a patient does not have a routine care visit at the given visit, the scale will be administered by phone.

^gData collected will be collected CCI at completion of the study (plus 3 months to allow for lag in CCI patient data from baseline through end of study will be included. CCI

3.5.3 Assessments (Main and Exploratory Studies)

3.5.3.1 Adverse Events

Refer to [Section 4](#) (Reporting of Adverse Events).

CCI [REDACTED]

[REDACTED]

[REDACTED]

[REDACTED]

[REDACTED]

[REDACTED]

[REDACTED]

[REDACTED]

[REDACTED]

[REDACTED]

[REDACTED]

[REDACTED]

[REDACTED]

[REDACTED]

[REDACTED]

[REDACTED]

[REDACTED]

[REDACTED]

[REDACTED]

[REDACTED]

[REDACTED]

[REDACTED]

[REDACTED]

[REDACTED]

[REDACTED]

[REDACTED]

[REDACTED]

[REDACTED]

[REDACTED]

[REDACTED]

[REDACTED]

[REDACTED]

[REDACTED]

The virtual matched control group is not applicable for the exploratory study.

3.5.5 End of Study

The End of Study Date is defined as the last Date of Contact or the Date of Final Contact Attempt for the last patient completing or withdrawing from the study, plus a 3-month lag time to allow for CCI XXXXXXXXXX

The End of Study Date will be the last date overall (main study or exploratory study).

3.6 Stopping Rules, Withdrawal Criteria, and Procedures

3.6.1 Entire Study

Otsuka and/or the IRB/IEC reserve the right to terminate the study at any time. In this event, all data collection will end. After the collected data is received, study physicians will be compensated as contractually agreed. If Otsuka terminates or suspends the study for safety or unanticipated other reasons, prompt notification will be given to study sites, IRBs/IECs, and regulatory authorities in accordance with regulatory requirements.

3.6.2 Individual Site

The IRB/IEC reserves the right to terminate participation of individual study sites at any time. Individual study sites may also be terminated for cause by Otsuka per contractual agreement. In such cases, all data collection at terminated study sites will end. After the collected data is received, the study physicians will be compensated as contractually agreed.

The sponsor should be notified promptly if the study is terminated by the physician or the IBR/EC at the site.

3.6.3 Individual Patient

Patient withdrawal from the study will be based upon physician clinical determination and/or patient decision. Participation in the study is voluntary, and all patients are free to terminate their participation at any time. In the event of study withdrawal, the study physician will record the reason for study withdrawal and continue to follow-up with the patient for any unresolved SAEs. Upon patient withdrawal from the study, all data collection will end, but all study data collected up to withdrawal will be included in the study database.

In addition, patients falling under the following criteria must be withdrawn from the study:

- occurrence of any intercurrent illness or abnormality in a laboratory assessment which, in the opinion of the physician, warrants the patient's permanent withdrawal from the study;
- at the request of the patient or physician;
- patient becomes pregnant; or
- patient is lost to follow-up.

3.6.4

CCI

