3.3.1 Informed Consent

An informed consent form (ICF) fully describing the purpose, procedures, and potential risks and benefits of the study will be developed and approved by the Institutional Review Board / Independent Ethics Committee (IRB/IEC) prior to study initiation. The study physician must ensure that each study patient is fully informed of the study and authorizes release of health information prior to study enrollment. Written informed consent will be obtained prior to initiation of any study-related procedures. The patient will receive a copy of the signed ICF. The study physician will retain the original signed ICF for each patient. The IRB/IEC must prospectively approve the ICF and any changes to the ICF during the course of the study before use.

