^cAll patients will complete the Day 180 visit. If a patient withdraws or is withdrawn from the study prematurely (eg, before completing the scheduled Day 180 visit), then an early ET visit should be performed, at which time all assessments and procedures that were to have been performed at the Day 180 visit should be completed. In such cases, the reason for the ET must be recorded.

^dAt the Day 180 visit, a second, optional interventional period (up to 6 months of Abilify MyCite; Days 180-≤360) may be initiated per the joint decision of the patients with their study physician. If the patient is not continuing in the optional second Abilify MyCite treatment period (Days 180-≤360), then the Day 180 visit is the final visit. Patients need to be on aripiprazole to use the system for the optional second treatment period.

^eThe Day 360 visit (and activities) are only completed for patients in the optional second Abilify MyCite treatment period (Days 180-≤360). If a patient withdraws or is withdrawn from the study prematurely (eg, before completing the scheduled Day 360 visit), then an early ET visit should be performed, at which time all assessments and procedures that were to have been performed at the Day 360 visit should be completed. In such cases, the reason for the ET must be recorded.

^fThe study physician is expected to regularly review the Abilify MyCite dashboard data during active Abilify MyCite use as consistent with routine care, approximately every 2 weeks. Note that “---x---” indicates an activity that occurs multiple times during the period.

^gIf a patient does not have a routine care visit at Day 30, Day 60, or Day 90, the scale will be administered by phone.

^hData collected if available per routine clinical practice ^{CCI} [REDACTED] at completion of the study (plus 3 months to allow for lag in ^{CCI} [REDACTED] patient data from baseline through end of study will be included. ^{CCI} [REDACTED]

3.5.1.1

CCI [REDACTED]

[REDACTED]

Data will also be collected from a virtual matched control group, as described in [Section 3.5.4](#).

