- ≥ 180 days of medical and pharmacy enrollment following index date

Prior to matching, the pool of potential controls and the Abilify MyCite cohort will be stratified by psychiatric diagnosis (SCH, BP1, MDD). The Abilify MyCite cohort psychiatric diagnosis will be based on the psychiatric diagnosis recorded in the eCRF. The potential controls psychiatric diagnosis will be based on the psychiatric diagnosis identified [REDACTED] CCI. In the event that more than one of the qualifying psychiatric diagnoses is identified [REDACTED] CCI, the following hierarchy will be applied to potential controls: SCH>BP1>MDD.

From this pool of patients, combined with the active arm, logistic regression will be used within each psychiatric diagnosis to estimate a propensity score for each patient, where propensity refers to a patient's pre-index likelihood to be in the active arm. The dependent variable equals 1 for patients in the active arm and 0 for the controls. The following variables may be considered for inclusion in the propensity score model; a final determination will be made using descriptive study results on patient baseline characteristics.

- Age
- Gender
- Month of index date
- Plan type (commercial, Medicaid, or Medicare health plan with medical and pharmacy benefits)
- Number of fills for any atypical antipsychotic over 6-12 months prior to index date
- [REDACTED] CCI
- Occurrence/number of visits with a psychiatrist over 6-12 months prior to index date
- Comorbidities over 6-12 months prior to index date

¹⁶ Defined as a medical claim with place of service code = 52 ("Psychiatric Hospitalization"), or with HCPCS codes H0035 or S0201.

- Region of patient residence (Northeast, South, Midwest, West)

The estimated propensity scores will be used to match active arm patients to the virtual controls in a 1:3 ratio. Prior to assessing outcomes, the validity of the propensity score adjustment will be assessed by (1) graphically examining the overlap in propensity scores across treatment and control groups¹⁷, and (2) comparing balance in all baseline characteristics across the cohorts via standardized mean differences. A standardized mean difference >10% in absolute value will be used to indicate potential imbalance that may warrant further investigation or adjustment (e.g. through regression analysis).¹⁸ Propensity score models will be finalized prior to the assessment of outcomes.

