5.1.2 Analysis Population

The analysis population includes all patients who met all of the inclusion criteria and none of the exclusion criteria and completed a Day 180 study visit.

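### Hospitalization data stop at withdrawal in the MyCite arm only, so Day 180 status may be missing for up to the planned 30%, with a bias that is plausibly but not certainly downward

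*Protocol*

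**What the plan says.** **MyCite arm.** Protocol 3.6.3 rules that "Upon patient withdrawal from the study, all data collection will end", while "all study data collected up to withdrawal will be included in the study database". The mandatory withdrawal criteria there include the case where the "patient is lost to follow-up", so that patient falls under the same rule. Protocol 3.6.2 adds that "all data collection at terminated study sites will end".

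**Control arm.** SAP 3.4 admits a control only with "≥ 180 days of medical and pharmacy enrollment following index date". A control's 180-day outcome is therefore complete by construction.

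**Source of the endpoint data.** Every enrolled patient is a member of an affiliated plan with medical and pharmacy benefits (Protocol 3.3.4, criterion 1) and "authorizes release of health information prior to study enrollment" (Protocol 3.3.1). In Table 3.5.1-1, hospitalizations sit in a Days 1-360 column. Footnote h to that row, partly redacted, has the data collected at study completion plus a 3-month lag and says that "patient data from baseline through end of study will be included". Protocol 3.5.5 defines the End of Study Date for the study as a whole, not for each patient.

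**Analysis.** SAP 5.1.2 restricts the analysis population to eligible patients who "completed a Day 180 study visit". The SAP's missing-data section does not impute and leaves missing values out of percentages. SAP 3.4 nevertheless mentions early-termination data being collected before matching, which leaves open whether patients who terminate early are matched.

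**The concern.** The primary endpoint is whether a patient was hospitalized by Day 180. It does not need a site visit, since all patients are plan members and a data extraction is already scheduled. Section 3.6.3 nonetheless makes leaving the study the end of collection. The sample-size sections expect 30% dropout, about 192 of 640 MyCite patients. No such gap arises among controls.

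This differs from the choice of analysis set. Moving to an all-enrolled analysis would not help if admissions after withdrawal were never collected. Collecting them would not help if SAP 5.1.2 still removed patients without a Day 180 visit. Both must change together. At stake is a 7.26-point design difference that missing outcomes in one arm could mimic or mask.

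**Working it through.** **Inputs.** From Protocol 7.1 and SAP 4.2: 36.30% control, 29.04% MyCite (difference 7.26 points), 1:3 matching, 80% power, significance level 0.025, 447 completers, 30% dropout, 640 enrolled. Protocol 7.3.1 and SAP 4.4 make the test one-sided. Dropout timing and the dropouts' true rate are not in the documents and are assumed below.

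**The plan's own figures.** The pooled two-proportion formula gives 441 MyCite patients, close to 447. The unpooled form that the plan names gives 422, or 440 with a continuity correction. Inflation gives 447/0.70 = 639, against 640 stated. The control count is 3 × 447 = 1,341, stated as about 1,350.

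**Case 1: completers only, as SAP 5.1.2 has it.** Suppose there is no true effect, so the whole MyCite arm has a rate of 36.3%. If dropouts have true 180-day rate r, the completer rate is (0.363 − 0.3r)/0.7. At r = 45% this is (0.363 − 0.135)/0.7 = 32.6%. The last column is the chance that a one-sided 0.025 unpooled Z-test favours MyCite, with 447 v 1,341 patients.

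| Assumed r | Completer rate | Bias (points) | Chance of a false positive |
|---|---|---|---|
| 25% | 41.1% | +4.8 | near 0 |
| 36.3% | 36.3% | 0 | 2.5% |
| 45% | 32.6% | −3.7 | about 30% |
| 53.2% | 29.1% | −7.2 | about 82% |

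The value of r that reproduces the design effect exactly is (0.363 − 0.7 × 0.2904)/0.3 = 53.24%. In this case, hospitalizations recorded before withdrawal are also lost to the analysis.

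**Case 2: all enrolled, data cut at withdrawal, unseen events counted as none.** The plan does not specify this analysis, but it is what an all-enrolled analysis would face while 3.6.3 stands. Assume no true effect, a constant hazard and the same risk in dropouts.

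- Hazard: λ = −ln(1 − 0.363)/180 = 0.4510/180 per day.
- Withdrawal uniform over 180 days: the mean of 1 − exp(−λt) is 1 − 0.363/0.4510 = 19.5%.
- Observed MyCite rate: 0.7 × 36.3% + 0.3 × 19.5% = 31.3%, a bias of −5.0 points, or 5.04/7.26 = 69% of the design effect.
- With 640 v 1,920 patients (3 × 640), the unpooled SE is 0.02136 and 0.0504/0.02136 = 2.36. P(Z > 1.96 − 2.36) is about 65% (64% with a pooled null variance).
- If all leave at Day 135: dropouts show 28.7%, the arm shows 34.0%, the bias is −2.3 points and the false-positive rate is 18%.

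These calculations treat the arms as independent, as Protocol 7.3.1 does. SAP 4.4 names McNemar's test, which would change the rejection probabilities somewhat but not the bias.

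**The case against.** **The tempting stronger reading is that the MyCite rate is certain to be biased downward.** A reader might infer this from 3.6.3 alone. It requires withdrawn patients to stay in the denominator as event-free. SAP 5.1.2 and the missing-data rule remove them instead, so the direction depends on r. A higher risk in dropouts is plausible, since intercurrent illness and loss to follow-up are withdrawal criteria, but no figure in the documents establishes it. The 5.0-point and 65% results belong to Case 2 only, and 640 v 1,920 is not a comparison that the plan makes.

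**The data may in fact exist.** Footnote h with the study-level End of Study Date can be read as carrying hospitalization data past an individual's withdrawal. Section 3.6.2 does not clearly stop plan-data extraction for patients at a closed site. Section 3.6.4, most of 3.5.1.9 and parts of footnote h are redacted and could address this. So one cannot say that post-withdrawal outcomes will not be available. One can say that the visible rule in 3.6.3 is explicit and that footnote h does not visibly make an exception to it.

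**Some follow-up continues after withdrawal.** Unresolved SAEs (3.6.3), pregnancies and infants (4.5), and product-associated SAEs after last contact (4.6.1) are followed. The early-termination visit brings the Day 180 assessments forward. None of these captures every later admission up to Day 180.

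**The 30% is not described as consisting only of 3.6.3 withdrawals.** That is correct, so 30% is an upper figure for the missing share due to this rule at the planned dropout rate. Passive data also cannot cover patients who lose plan coverage.

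**Conclusion.** The point holds as an unreconciled conflict about ascertainment of the primary endpoint. Protocol 3.6.3 ends collection at withdrawal in the MyCite arm, footnote h with 3.5.5 may continue it, and controls are fully observed by rule. If 3.6.3 governs, Day 180 status may be missing for up to 30% of one arm.

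Under the SAP's own population the resulting bias runs from +4.8 to about −7.2 points for assumed dropout rates of 25% to 53.2%. It is zero only if dropouts and completers share the same risk. If all enrolled patients were analysed with data cut at withdrawal, the bias would be downward, between −2.3 and −5.0 points for the two timings shown.

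Controls are also selected on completing 180 days, but by insurance enrollment rather than by a visit, so the two arms are filtered by different rules. SAP 5.0 reports that the study stopped after two patients without an efficacy assessment. The point therefore bears on the plan and any reuse of it.

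**What to change.** 1. In Protocol 3.6.2 and 3.6.3, separate three events: stopping MyCite, ending site contact, and withdrawing permission to use plan data. Only the third should end collection of hospitalization and pharmacy data.
2. In all other cases, including loss to follow-up and site termination, continue passive plan-data collection through Day 180 and say so in the consent form. Bring footnote h and 3.5.5 into line with this.
3. Amend SAP 5.1.2 so that the primary analysis includes all eligible enrolled patients who started MyCite, with hospitalizations counted to Day 180 whether or not the Day 180 visit took place. State in SAP 3.4 that patients who terminate early are matched.
4. Add a sensitivity analysis for patients who withdraw data permission or lose plan coverage, for example over a range of r as in the working.

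The cost is protocol, consent-form and SAP wording. No extra visits are needed, because the extraction with its 3-month lag is already planned. Some patients may decline permission or lose coverage and will remain missing.
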